11.5. Appendix 5: Derived and Transformed Data

11.5.1. General

Multiple Measurements at One Time Point

- Mean of the measurements will be calculated and used in any derivation of summary statistics but if listed, all data will be presented.
- If there are two values within a time window the value closest to the target day for that window will be used. If values are the same distance from the target then the mean will be taken. Generally, nominal visit is used in this study and this rule would not apply then.
- Subjects having both High and Low values for Normal Ranges at any post-baseline visits for safety parameters will be counted in both the High and Low categories of “Any visit post-baseline” row of related summary tables. This will also be applicable to relevant Potential Clinical Importance summary tables.

Study Day

- Calculated as the number of days from the date of first dose of study treatment:
 - Ref Date = Missing → Study Day = Missing
 - Ref Date < Date of First Dose → Study Day = Ref Date – Date of First Dose
 - Ref Date ≥ Date of First Dose → Study Day = Ref Date – (Date of First Dose) + 1

Note: Date of first dose is Day 1 and the day before the date of first dose is Day -1 (there is no Day 0).

11.5.2. Study Population

Demographics and Baseline Characteristics

Age

- Only birth year is collected in the eCRF; birth day and month will be imputed as ‘30th June’.
- Birth date will be presented in listings as ‘YYYY’.
- Age, in whole years, will be calculated with respect to the date of randomisation using the imputed date of birth
- For subjects not randomised, age, in whole years, will be calculated with respect to the baseline visit date if visit done and date is available, and with respect to screening visit date otherwise.

Age Ranges

- The demographic summary table will include the standard age ranges: ≤ 18 years, 19 to 64 years, ≥ 65 years.
- The summary of age ranges table will include only the Adult (18 to 64 years) category
- These are standard categories and cannot be changed, even though the study age range is 18 to 30 years (inclusion criteria).

Body Mass Index (BMI)

- Calculated as $\text{Weight (kg)} / [\text{Height (m)}]^2$

Demographics and Baseline Characteristics	
Race	

 The five high level FDA race categories and two designated Asian subcategories are: 
 1) American Indian or Alaska Native 2) Asian 
 a) Central/South Asian Heritage b) Japanese Heritage/East Asian Heritage/South East Asian Heritage 3) African American/African Heritage 4) Native Hawaiian or Other Pacific Islander 5) White 
 Note: subjects may report more than one race category in the CRF. This will be handled as follows in summary tables. A subject will only be represented in a single category. A subject who selects a combination of races will be counted as either "MIXED ASIAN RACE", "MIXED WHITE RACE" or "MULTIPLE" (depending on the race categories selected) but not in each of the constituent terms. Therefore the counts will add up to the total number of subjects with a response, and the percentages will add to 100%. 	
Baseline HbA1c	

 Baseline HbA1c categories are (%): $\leq 6.5\%$, > 6.5 to 7.0%, > 7.0 to 8.0%, > 8.0 to 9.0%, $> 9.0\%$ 	
Time from Diagnosis to First Dose of Study Treatment	

 The time from diagnosis to first dose of study drug is calculated as the days lapsed between date of first dose and Type 1 diabetes diagnosis date: $\text{Date of first dose} - \text{Diagnosis date}$ Time from diagnosis categories will be (days): 28-42; 43-56; > 56. 	
Presence of T1DM associated antibodies	

 The following antibodies are assessed at baseline and at Week 4, Week 16, Week 28, Week 40, Week 52 and Week 64: antibody to glutamic acid decarboxylase (anti-GAD); antibody to protein tyrosine phosphatase-like protein (anti-IA-2); and insulin autoantibody (IAA). Only baseline data will be summarised. For each antibody the baseline data will be classed as positive or negative. Numeric results will be available from the central laboratory dataset. These numeric results will be translated into the positive/negative classification based on the Normal Range High value provided for each test (LBORNHRI): 
 $<$Normal Range High value: Negative \geqNormal Range High value: Positive Note, for anti-GAD the test was performed using two different test kits 1) old RIA test kit (units KU/L) and 2) new ELISA test kit (units IU/ML). And therefore has different Normal Range High values depending on which test kit was used. Summaries of T1DM associated antibodies (anti-GAD, anti-IA-2, IAA) will only include data from the central laboratory 	

Demographics and Baseline Characteristics	
Number of Positive Type 1 Associated Antibodies: Anti-GAD/Anti-IA-2/IAA and Anti-GAD/Anti-IA-2 (excluding IAA)	

 The number of positive type 1 associated antibodies will be calculated for each subject using all three antibodies: anti-GAD, anti-IA-2 and IAA. Categories will be 1, 2 or 3. The number of positive type 1 associated antibodies will also be calculated for each subject using two of the three antibodies: anti-GAD and anti-IA-2. IAA will not be included. Categories will be 1 or 2. 	
DEFEND-1 Demographic and Baseline Characteristics	

 Age at screening will be used from the DEFEND-1 datasets. BMI will be used from the DEFEND-1 datasets. Time from diagnosis to first dose of study drug will be calculated as described above. Baseline HbA1c will be categorized as described above The presence of type 1 associated antibodies will be reported for anti-GAD and anti-IA-2 (positive/negative) The number of positive type 1 associated antibodies will be reported using anti-GAD and anti-IA-2 results (categories 0/1/2) 	
Extent of Exposure	
Duration of Exposure (including breaks)	

 Number of days of exposure to study drug will be calculated based on the formula: Duration of Exposure in Days = Treatment Stop Date – (Treatment Start Date) + 1 Subjects who were randomised but did not report a treatment start date will be categorised as having zero days of exposure. Duration of exposure categories will be: ≤ 8 weeks; >8 weeks to ≤ 12 weeks; >12 weeks to ≤ 24 weeks; >24 weeks to ≤ 40 weeks; >40 weeks to ≤ 52 weeks; >52 weeks. Subjects will be assigned to categories using exposure calculated in days: 
 ≤ 8 weeks: ≤ 56 days >8 weeks to ≤ 12 weeks: >56 days to ≤ 84 days >12 weeks to ≤ 24 weeks: >84 days to ≤ 168 days >24 weeks to ≤ 40 weeks: >168 days to ≤ 280 days >40 weeks to ≤ 52 weeks: >280 days to ≤ 364 days >52 weeks: >364 days Total person time on treatment (years) will be calculated using: Total person time on treatment = $([Treatment\ Stop\ Date - Treatment\ Start\ Date + 1] + 56) / 365.25$ Note: safety data for events that occurred up to 56 days after the last dose of study medication are included as 'on-therapy' – this period was chosen in consideration of the long half-life of albiglutide. 	
Duration of Exposure (excluding breaks)	

 Duration of exposure excluding breaks will be calculated as: (Treatment Stop Date – Treatment Start Date + 1) – (7 * number of missed doses). Duration of exposure categories will be assigned as defined above. Total person time on treatment (years) excluding breaks will not be derived or presented. 	

Extent of Exposure
Duration of Exposure by Actual Dose Level

 The albiglutide dose in this study will start at 30-mg weekly and be increased to 50-mg weekly at Week 6 if the patient is able to tolerate the 30 mg weekly dose. Subjects experiencing GI intolerance on the 50 mg dose may decrease back to the 30 mg dose following discussion between the investigator and the medical monitor. For albiglutide subjects, the duration of exposure by actual dose level will be calculated as the number of days on 30mg study treatment and the number of days on 50mg study treatment as follows: 
 For subjects who do not up-titrate: 
 Duration of exposure to 30mg = duration of exposure (days) Duration of exposure to 50mg = 0 For subjects who up-titrate, with no subsequent down-titration: 
 Date of up-titration = date of first dose of 50mg IP Duration of exposure to 30mg = (date of up-titration-1) – date of first dose 30mg IP + 1 Duration of exposure to 50mg = date of last dose IP (50mg) – date of first dose 50mg IP +1 For subjects who up-titrate, but subsequently down-titration back to 30mg: 
 Date of up-titration = date of first dose of 50mg IP Date of down-titration = date of first dose 30mg IP after 50mg IP Duration of exposure to 30mg (1) = (date of up-titration-1) – date of first dose 30mg IP + 1 Duration of exposure to 30mg (2) = date of last dose IP (30mg) – date of down-titration +1 Duration of exposure to 30 mg = Duration of exposure to 30 mg (1) + (2) Duration of exposure to 50mg = (date of down-titration-1) – date of up-titration + 1 Note: for all patients the total duration of exposure should equal duration of exposure to 30mg + duration of exposure to 50mg. Note: similar rules will be applied for any subjects who do not follow the standard titration plan. For placebo patients, the duration of exposure by actual dose level will not be calculated. Categories for duration of exposure by actual dose level will be as described for total duration of exposure. Total person time on treatment (years) will be calculated for each actual dose level as: 
 For each albiglutide subject, for the last actual dose level received the duration of exposure to 30mg/50mg (days) will have 56 days added. The duration of exposure to 30mg/50mg (days) will then be summed across subjects and converted into years by dividing by 365.25.

Extent of Exposure
Compliance

 Treatment compliance will be calculated for each subject as the total number of doses actually taken (numerator) divided by the number of doses that should have been taken (denominator), multiplied by 100. Compliance will be calculated based on information recorded on the study treatment eCRF (using date of first dose, date of last dose and missed dose information to determine compliance) 
 Numerator = ceiling[(date of last dose – date of first dose +1)/7] – number of missed weekly doses Denominator = ceiling[(date of last dose – date of first dose +1)/7] 
Where ceiling [x] = smallest integer $\geq x$
 
Note: numerator/denominator are in terms of weeks of treatment
 Categories of treatment compliance will be created as follows: missing, <80%, $\geq 80\%$

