The half-life of albiglutide is approximately 5 days, and significant therapeutic concentrations can persist for up to 5 half-lives (3 to 4 weeks) after discontinuation. Therefore, the investigator should use caution when prescribing treatment after the withdrawal of active study medication taking into consideration the long half-life of albiglutide (see Section 5.6.2 for prohibited anti-diabetic medications for subjects discontinuing study medication early but still participating in the study), taking into consideration the long half-life of albiglutide.

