11.3.2.1. Treatment States for AE Data

Treatment State	Definition
Pre-Therapy	The onset date of the AE is before the treatment start date. AE Start Date $<$ Study Treatment Start Date
On-Therapy	If AE onset date is on or after treatment start date & on or before treatment stop date + 56 days. Study Treatment Start Date \leq AE Start Date \leq Study Treatment Stop Date + 56 days
Post-Therapy	If AE onset date is after the treatment stop date + 56 days. AE Start Date $>$ Study Treatment Stop Date + 56 days
Onset Time Since 1 st Dose (Days)	If Treatment Start Date $>$ AE Onset Date = AE Onset Date – Treatment Start Date If Treatment Start Date \leq AE Onset Date = AE Onset Date – Treatment Start Date +1 Missing otherwise.
Duration (Days)	AE Resolution Date – AE Onset Date + 1
Drug-related	The relationship question on the CRF 'Is there a reasonable possibility that the AE may have been caused by the Study Treatment?'. The investigator additionally specifies if this is in relation to blinded study medication (albiglutide/placebo) or Insulin. The AE will be considered to be drug-related if the relationship is marked 'YES' and it is marked as related to blinded study medication (albiglutide/placebo). If the AE is marked as related to insulin only it will not be included as drug-related. If a relationship to the study drug is missing or unknown, after the start of treatment, it will be assumed for the purpose of analyses to be drug-related.

NOTES:

- If the study treatment stop date is missing then the AE will be considered to be On-Therapy.

11.3.2.2. Treatment States for Subject-Reported Hypoglycaemic Events, Medication and Non-Drug Therapy Data

Treatment states for subject-reported hypoglycaemic events, medications and non-drug therapy data are assigned according to the same rules as AE data.

Treatment State	Definition
Pre-Therapy	The onset date of the event/medication is before the treatment start date. Event/Medication Start Date < Study Treatment Start Date
On-Therapy	If event/medication onset date is on or after treatment start date & on or before treatment stop date + 56 days. Study Treatment Start Date ≤ Event/Medication Start Date ≤ Study Treatment Stop Date + 56 days
Post-Therapy	If event/medication onset date is after the treatment stop date + 56 days. Event/Medication Start Date > Study Treatment Stop Date + 56 days

NOTES:

- If the study treatment stop date is missing then the assessment will be considered to be On-Therapy

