- The mean of the triplicate measurements at each visit will be used in these summaries.
- Data for QTc (other method of correction) will also be presented as a separate parameter in these summary tables.

Adverse Events

AE Density

- AE density, also referred to as event density, will be calculated as the number of events in a given period divided by the total person time on treatment (in years) of subjects at risk at the beginning of the same period. All AE densities will be presented per 100 person-years (by multiplying the above defined statistics by 100). i.e.:
- On-therapy AE density = 100 x number of on-therapy AEs/total person time on treatment (years)
- Note: see exposure derivations for total person time on treatment calculation.

AE's of Special Interest

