
 Summaries of subject-reported events over time will calculate percentages based on the number of subjects at risk of an event within each time period. i.e., the Ns will be expected to decrease over time as subjects withdraw from the study The date of study withdrawal will be used as the end-date of the 'at-risk' period for each subject, as subject-reported hypoglycaemic events are reported throughout the study period i.e., until week 64 or study withdrawal. A subject will not be included as 'at-risk' in a particular period if their study withdrawal date is before the start date of the interval.
Hypoglycaemic Events with Glucose $<3.1\text{mmol/L}$

 Hypoglycaemic events with a plasma glucose $<3.1\text{ mmol/L}$ ($<56\text{ mg/dL}$) will also be identified.
Laboratory Parameters
Only data from the central laboratory will be included in the tables, figures and listings. Data from local laboratories will not be included.
eGFR

 $\text{eGFR} (\text{mL/min}/1.73\text{ m}^2) = 175 \times (\text{S}_{\text{cr}})^{-1.154} \times (\text{Age})^{-0.203} \times (0.742 \text{ if female}) \times (1.212 \text{ if African American})$ eGFR will be calculated based on measured creatinine and associated age. For this purpose, associated age (in whole years) will be calculated with respect to the date of creatinine sample using the imputed date of birth (see Section 11.6.2.1). This derived eGFR will be used for summary tables.
Glucose data not included in laboratory TFLs

 Glucose readings from the MMTT will not be included in any laboratory TFLs. These are identified in SDTM.LB as LBTEST='Glucose' and LBTPTNUM = 10, 20, 30, 40, 50, 60, 70. Finger-stick glucose readings for the MMTT will not be included in any laboratory TFLs. These can be identified in the SDTM.LB dataset using LBTEST='Glucose' and VISIT ne " and LBNAM='NOT APPLICABLE - NO RANGES EXPECTED', LBTPPT=' ' and LBSPEC='BLOOD'. Glucose data from the eDiary card and 72h CGM will not be included in any laboratory TFLs. The glucose data from the eDiary and 72h CGM can be identified in the laboratory domain/dataset (SDTM.LB) as LBTEST = "Glucose" and LBNAM="NOT APPLICABLE – NO RANGES EXPECTED". 
 Subject reported Hypoglycaemic event glucose readings are identified where LBTPT

Laboratory Parameters

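### AE density counts a full 56 days after the last dose as time at risk even for subjects who have left the study, so the rates come out slightly low

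*SAP*

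**What the plan says.** SAP 11.5.2 (Extent of Exposure) computes each subject's total person time from the treatment start and stop dates, with the formula ending "Date + 1] + 56) / 365.25". The reason given is that "safety data for events that occurred up to 56 days after the last dose of study medication are included as" on-therapy. For exposure by actual dose level the same section repeats the addition: for the last dose level received, "the duration of exposure to 30mg/50mg (days) will have 56 days added".

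SAP 11.5.3 then defines "On-therapy AE density = 100 x number of on-therapy AEs/total person time on treatment (years"), and describes the denominator as the time "of subjects at risk at the beginning of the same period". The numerator follows SAP 11.3.2.1, where an AE is on-therapy under the rule "If AE onset date is on or after treatment start date & on or before treatment stop date + 56 days". Density is reported by treatment group in the AE overview (SAP 8.2.1.1) and for each on-therapy AESI (SAP 8.2.1.7).

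None of these sections ends person-time at study withdrawal, death or last contact. For subject-reported hypoglycaemia by time period, SAP 11.5.3 does bring in study exit: "The date of study withdrawal will be used as the end-date of the" at-risk period.

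**The concern.** A rate per person-year is sound only if events could be recorded during the time in the denominator. Protocol 6.4.21 collects AEs from the start of treatment to the follow-up contact. Under Protocol 4.4 a subject who withdraws from the study stops attending visits, after an early withdrawal visit held as soon as possible. No safety contact at 56 days is specified for that subject. Days after exit therefore enter the denominator in full, while the numerator has no planned source of events for them.

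The error has one direction: the density is too low wherever subjects leave the study within 56 days of the last dose. If more subjects leave early in one arm, that arm's AE and AESI rates are lowered more than the other's.

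**Working it through.** The documents give no person-time total and no AE density, so there is no stated figure to reproduce. The check applies the SAP formula and compares it with the same formula stopped at study exit.

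**Inputs from the documents**
- 68 subjects, 51 albiglutide and 17 placebo (Protocol 3.1).
- 10% drop-out (Protocol 8.2.1). As a check, 60/0.90 = 66.7, in line with approximately 68.
- 52 weeks of treatment = 364 days, then 12 weeks of follow-up = 84 days (Protocol 3.1). Since 84 > 56, a completer's added time is fully observed.

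**Assumptions (not in the documents)**
- Every drop-out leaves the study, not only the drug.
- The last dose of early leavers falls at day 56 or day 182, and exit is on that day or 28 days later.

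**Formulas**
- SAP days = completers × (364 + 56) + leavers × (last-dose day + 56).
- Observed days = completers × 420 + leavers × (last-dose day + days from last dose to exit, at most 56).
- Understatement of density = 1 − observed/SAP.

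**Each subject who leaves at the last dose:** 56/365.25 = 0.153 unobserved person-years.

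**10% leaving, last dose at day 182:** 6.8 leavers and 61.2 completers.
- SAP: 61.2 × 420 + 6.8 × 238 = 25,704 + 1,618.4 = 27,322.4 days = 74.80 person-years.
- Observed, exit at last dose: 25,704 + 6.8 × 182 = 26,941.6 days = 73.76 person-years. Understatement 1.39%.
- Observed, exit 28 days later: 25,704 + 6.8 × 210 = 27,132 days = 74.28 person-years. Understatement 0.70%.

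**Other leaving rates**

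| Leaving | Last dose | Exit | SAP person-years | Observed person-years | Density too low by |
|---|---|---|---|---|---|
| 0% | – | – | 78.19 | 78.19 | 0% |
| 5% | day 182 | at last dose | 76.50 | 75.98 | 0.68% |
| 20% | day 182 | at last dose | 71.42 | 69.33 | 2.92% |
| 30% | day 182 | at last dose | 68.03 | 64.90 | 4.60% |
| 30% | day 56 | at last dose | 60.99 | 57.86 | 5.13% |

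**Between arms (exit at last dose).** The albiglutide/placebo density ratio is multiplied by (1 − albiglutide understatement)/(1 − placebo understatement):
- 10% in both arms: 1.000.
- 20% albiglutide, 5% placebo: 0.9775 (last dose day 182) or 0.9755 (day 56).
- 30% albiglutide, 0% placebo: 0.9540 (day 182) or 0.9487 (day 56).

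**The case against.** The strongest reply is that few subjects are affected and the result is descriptive. Protocol 4.4 separates stopping drug from leaving the study: subjects who stop are asked to attend the MMTT visits through Week 64, where AEs are assessed. Gastrointestinal intolerance can also be handled by blinded dose reduction. Protocol 8.3.5.4 plans no inferential testing of safety variables, and the main AE tables give numbers and percentages of subjects, which do not use this denominator. All of this stands, and it limits the size and consequence of the point.

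The Study Procedures Manual holds the procedures for post-study AEs (Protocol 6.4.23) and is not available, so some events after exit may be captured. That could narrow the gap, but a procedure for post-study events does not turn those days into planned follow-up.

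The hypoglycaemia rule in SAP 11.5.3 is not an exact precedent. It sets the number of subjects at risk in each interval, and a subject drops out of the count only if withdrawal precedes the start of the interval. It shows that the SAP treats study exit as ending risk elsewhere, but it is not person-time censoring.

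Three stronger readings are tempting and not supported:
- A reader might take the effect on a single early leaver as the size of the problem. That subject's own rate is halved if the last dose is on day 56 (56/112), but density is reported only by treatment group.
- A reader might infer that AE rates at 30 mg are diluted through the dose-level rule. SAP 4.3 confines dose-level summaries to certain exposure tables, and no AE density by dose is planned.
- A reader might argue that 56 days is too long, because Protocol 4.4 says "significant therapeutic concentrations can persist for up to 5 half-lives (3 to 4 weeks) after discontinuation". The numerator uses the same 56-day window, and the error lies in counting unobserved days, whatever the length of the window.

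**Conclusion.** The denominator rule is wrong as written for subjects who leave the study within 56 days of the last dose, and no other section corrects it. The reported on-therapy AE and AESI densities will be slightly too low: about 0.7% to 1.4% at the planned 10% drop-out, and up to about 5% if roughly 30% leave at the last dose. The leaving rates beyond 10%, the timing of last doses and the timing of exits are all assumed.

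A reader might infer that the rule favours albiglutide. The documents do not show that: they contain no data on early leaving by arm, and with equal leaving the ratio is unchanged. Under the assumed 20% against 5% it shrinks by 2.2% to 2.5%. This is a derivation error of low priority that does not affect the counts and percentages of subjects with AEs.

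**What to change.** In SAP 11.5.2, define each subject's person-time for AE density as:

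[min(treatment stop date + 56, date of last study contact at which AEs were assessed) − treatment start date + 1] / 365.25

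In SAP 11.5.3, count in the density numerator only on-therapy AEs with onset up to that same end date, so that events and time match. The on-therapy window in SAP 11.3.2.1 can stay as it is for the counts, percentages and listings. Apply the same cap to the 56 days added to the last dose level received, which affects exposure tables only.

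Using one named end date for every subject avoids a choice between withdrawal date and last contact after unblinding. The cost is one extra derivation from visit and call dates, and slightly higher densities where subjects left early. Completers' values do not change. The change should be made before unblinding.
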